7.2 SETTING

7.2.1 Secondary data source selection

The study will use administrative claims and EHR data from Optum's Market Clarity Integrated Claims + Clinical database.

7.2.2 Study population: Aim 1

The analysis for Aim 1 will include patients newly diagnosed with fibrosing ILD during the patient identification period. Patients must meet the following selection criteria to be included in the study:

Inclusion Criteria

- ≥ 2 fibrosing ILD diagnoses in any position on different dates of service, within 365 days of each other, and in the same continuous enrollment period during the patient identification period. The ***fibrosing ILD diagnosis date*** will be defined as the date of the first fibrosing ILD diagnosis. The two fibrosing ILD diagnosis codes can be one of the following combinations:
 - 2 fibrosis codes
 - 1 fibrosis code & 1 ILD code that requires fibrosis code
- ≥ 18 years of age as of the fibrosing ILD diagnosis date
- Continuous enrollment with medical and pharmacy coverage for 12 months prior to the fibrosing ILD diagnosis date (***pre-ILD baseline period***)

Exclusion Criteria

- Fibrosing ILD diagnosis in the 12-month pre-ILD baseline period
- Unknown gender or geographic region

Cohort Assignment

Patients meeting initial selection criteria for Aim 1 will be assigned to cohorts based on known cause of fibrosis:

- **IPF**— ≥ 2 medical claims with diagnosis for IPF in any position during the study period
- **Non-IPF ILD**— < 2 medical claims with diagnosis for IPF during the study period

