7.3 VARIABLES

Variables related to the study period will be defined as follows:

Aim 1

- **Fibrosing ILD diagnosis date**—The first ILD diagnosis date for patients with ≥ 2 fibrosing ILD diagnoses on different dates and within 365 days. The fibrosing ILD diagnosis date is the first day of follow-up observation time for Aim 1.
- **Pre-ILD baseline period**—The 12-month period prior to the fibrosing ILD diagnosis date.
- **Aim 1 follow-up period**—The variable period starting on the fibrosing ILD diagnosis date and continuing until the earliest of the following: disenrollment from the health plan, death, or end of the study period. The Aim 1 follow-up period will be used to assess Aim 1 outcomes.
 - **All-cause mortality**—Death will be used as a censoring event and is further defined in Section 7.3.3.1.

Aim 2

- **Index date**—For the oxygen therapy cohort, the first date following the fibrosing ILD diagnosis date with a claim with diagnosis for oxygen therapy; for the no oxygen therapy cohort, a date within the same continuous enrollment period as the fibrosing ILD diagnosis date that is similar to the matched oxygen therapy patient in time from fibrosing ILD to index date. The index date is the first day of follow-up observation time for Aim 2 and Further Aim.
- **Pre-index baseline period**—The 12-month period prior to the index date.
- **Aim 2 follow-up period**—The variable period starting on the index date until the earliest of the following: disenrollment from the health plan, death, or the end of the study period. Matched pairs will be given the same duration of follow-up. The Aim 2 follow-up period will be used to assess Aim 2 and Further Aim outcomes.
 - **All-cause mortality**—Death will be used as a censoring event and is further defined in Section 7.3.3.1.

An overview of the analytic study variables and the study periods for which each analytic variable will be reported is provided in Table 1. Additional variable information is provided in Sections 7.3.1 to 7.3.4.

Table 1. Analytic Variables by Data Source and Time Period

Characteristic	Data source		Aim 1 time period		Aim 2 time period	
	Claims*	EHR	Pre-ILD baseline	Follow-up	Pre-index baseline	Follow-up
Aim 1 outcomes						
Oxygen therapy (time to initiation, sustained oxygen therapy use)		X		X	X	
Aim 2 outcomes						
Disease progression	X	X				X
All-cause mortality	X					X
Hypoxemia	X	X	X		X	X
Acute exacerbations	X	X				X
Patient characteristics†						
Index year	X		X		X	

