7.3.1 Aim 1 Outcomes

7.3.1.1 Primary Outcomes

- **Oxygen Therapy**—Evidence of oxygen use will be captured in the pre-ILD baseline and Aim 1 follow-up periods based on the presence of ≥ 1 diagnosis (ICD-10-CM), procedure (HCPCS, CPT), or revenue code for oxygen therapy. Among patients with oxygen therapy in follow-up, the following aspects of oxygen therapy will be described:
 - **Time to oxygen therapy initiation**—The time in days from the fibrosing ILD diagnosis date to oxygen therapy initiation, among patients without evidence of oxygen therapy in the pre-ILD baseline period.
 - **Sustained oxygen therapy use**—Using claims, sustained oxygen therapy use will be defined among patients with at least 12 months of follow-up after the index date (oxygen initiation date), as a binary variable for the presence of ≥ 11 claims for oxygen therapy in a 12-month period. The following aspects of sustained oxygen therapy will be described:
 - **Time to sustained oxygen therapy use**—The time in days between the index date and the earliest date that defined the sustained oxygen therapy use.
 - **Sustained oxygen therapy use within the first 12 months of follow-up**—The number of patients with the evidence of sustained oxygen therapy use during the first 12 months of follow-up.
 - **Note:** As a sensitivity analysis, sustained oxygen therapy use will also be defined as ≥ 6 claims for oxygen therapy in a 12-month period and, based on the distribution of the count of claims among the population, as the 75th percentile of claims in a 12-month period.

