7.6.1 Aim 1 Analysis

7.6.1.1 Descriptive Analysis

All variables will be analyzed descriptively, and results will be stratified by cohort (IPF vs non-IPF ILD). Numbers and percentages will be provided for categorical variables. Means, medians, and standard deviations, will be provided for continuous variables. Appropriate statistical comparisons will be conducted based on the distribution of the measure.

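### The IPF label counts claims over the whole study period, so crude Aim 1 oxygen percentages by IPF stratum can differ through observation time alone

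*Combined protocol and SAP*

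**What the plan says.** Section 7.2.2 (Cohort Assignment), repeated in the abstract, defines the IPF cohort by at least two "medical claims with diagnosis for IPF in any position during the study period". Patients with fewer than two are non-IPF. The two diagnoses that qualify a patient for entry need not be IPF codes, so entry does not settle the label.

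Section 7.3 defines Aim 1 follow-up as "The variable period starting on the fibrosing ILD diagnosis date and continuing until the earliest of the following" of disenrollment, death or study end. No minimum is stated beyond the confirming diagnosis. By 7.1, entry runs from 01 October 2016 to 30 June 2022, and the study period ends on the same day unless it is extended.

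Section 7.3.1.1: "Evidence of oxygen use will be captured in the pre-ILD baseline and Aim 1 follow-up periods", on the basis of at least one code. Section 7.6.1.1 sets the stratification: "All variables will be analyzed descriptively, and results will be stratified by cohort (IPF vs non-IPF ILD". Categorical measures are to be summarised by counts with percentages. The same section then plans tests: "Appropriate statistical comparisons will be conducted based on the distribution of the measure".

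Section 7.6.1.2 analyses time to initiation by Kaplan-Meier, with censoring-adjusted percentages at fixed times such as 6, 9 and 12 months, and allows for competing events. Section 7.8 does not say that the label depends on how long a patient is observed.

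**The concern.** The label is settled by events after time zero, and non-IPF is the default. A patient with true IPF who dies, disenrolls or enters late may never accumulate two IPF claims. The labelled IPF stratum is therefore enriched for long observation and the non-IPF stratum for short observation. The chance of at least one oxygen code also rises with observation.

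Describing oxygen use is Aim 1 itself. A gap produced by unequal observation, accompanied by a test, would be read as a difference in oxygen use between IPF and other fibrosing ILD. Follow-up length and IPF share by index year would be distorted in the same way.

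**Working it through.** **No plan figure to reproduce.** The protocol gives feasibility counts but no oxygen, coding, death or disenrollment rates. All rates below are assumptions.

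**Inputs from the protocol.** Two-claim label over the study period (7.2.2); second fibrosing code within 365 days (7.2.2); variable follow-up (7.3); at least one oxygen code (7.3.1.1); entry window 01 October 2016 to 30 June 2022 (7.1), which is 2,098 days or 5.74 years.

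**Step 1: both quantities rise with time observed.** If IPF claims arise at rate L per year, P(two or more by time t) = 1 − exp(−Lt)(1 + Lt). With L = 1, this is 9.0% at 0.5 years, 26.4% at 1 year, 59.4% at 2 years and 80.1% at 3 years. At an oxygen hazard of 0.3 per year, the chance of at least one oxygen code is 1 − exp(−0.3t): 13.9% at 0.5 years, 25.9% at 1 year and 45.1% at 2 years.

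**Step 2: simulation with IPF unrelated to any outcome.** Base-case assumptions: 50% true IPF; a fibrosing code at time zero, then 4 fibrosing claims per year; 70% of codes in true IPF patients and 5% in others are IPF codes (so 4 × 0.7 = 2.8 later IPF claims per year in true IPF); oxygen 0.3, death 0.1 and disenrollment 0.2 per year; uniform entry over 5.75 years.

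| Base case, no true difference | Labelled IPF | Labelled non-IPF |
|---|---|---|
| Crude percent with oxygen | 43% | 36% |
| Median follow-up, months | 22 | 16 |
| 12-month 1 − Kaplan-Meier | 26% | 26% |

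The percentage is 39% in both true groups. Labelled IPF share is 54% in the first year of entry and 33% in the last six months. The Kaplan-Meier value agrees with 1 − exp(−0.3) = 25.9%.

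**Step 3: sensitivity of the crude gap, still with no true difference.**

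| Assumption changed | Crude gap, points |
|---|---|
| Grid of 24 settings: true IPF 30 or 50%; 2, 4 or 6 claims per year; IPF-code probability 50 or 90% in true IPF, 0 or 5% in others | 1 to 13 |
| Oxygen 1.5 per year for 3 months, then 0.2 | about 5 (51.0% vs 46.3%) |
| Oxygen 2 per year for 3 months, then 0.15 | 3.4 |
| 20% start at diagnosis, then 0.2 per year | 4.9 |
| IPF coding consistent within patient (beta-distributed probability, same means) | 3 to 5 |
| 90% of true IPF patients' codes are IPF codes, none in others | 1 to 2 |
| 12 more months of data after identification closes | 7 (49% vs 42%) |

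The extension repairs most of the index-year gradient (IPF share 48% versus 55%) but not the crude gap.

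**Step 4: person-year rates.** With a constant hazard they agree between strata (rate ratio 1.00). With front-loaded starts, the stratum followed longer accumulates more low-hazard time: 0.42 per year in labelled IPF versus 0.46 in labelled non-IPF, again with no true difference.

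**Step 5: an early-window label.** Take IPF as at least one IPF code by the second qualifying diagnosis, and start follow-up there among oxygen-free patients. The base case then gives 36% versus 36% and 16 versus 16 months. Misclassification at 50% prevalence is 0.5 × 0.3² + 0.5 × (1 − 0.95²) = 9.4%, against 8.6% under the present rule. Requiring two IPF codes by that date would give 0.5 × (1 − 0.7²) + 0.5 × 0.05² = 25.6%. About 15% of initiations precede the new start date under a constant hazard, but 42%, 49% and 54% do so under the three clustered-start settings in Step 3.

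**The case against.** The strongest reply is that the listed Aim 1 outcomes are time to initiation, time to sustained use and sustained use within 12 months. Initiation is already analysed by Kaplan-Meier at fixed times, and sustained use requires 12 months of follow-up after oxygen start. In the base case only 0.5% of true IPF patients in that subset are mislabelled, against 8.8% of true IPF patients overall. Whether crude percent with oxygen is tabulated and tested by stratum depends on the Annex 3 table shells, whose content is not in the available text.

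Most of this stands, and it narrows the point. It does not remove it: 7.3.1.1 captures oxygen use in follow-up, and 7.6.1.1 stratifies all variables by the label, gives percentages and plans comparisons.

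It is also fair to say that the gap could be small, and that an early-window label trades one error for another. Both are accepted.

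A reader might infer that the Kaplan-Meier or Cox results are biased as well. The documents do not support that in general. The Cox covariate list in 7.6.1.3 does not name the IPF label, and Kaplan-Meier by label is affected only if death, disenrollment or coding intensity is related to oxygen start.

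**Conclusion.** The point holds for crude stratified descriptions. The link between label and observation time follows from the definitions; only its size needs assumptions. With no true difference, the crude oxygen gap is about 1 to 13 points: about 7 in the base case, 3 to 5 with clustered starts or within-patient coding consistency, and 1 to 2 with nearly complete and specific IPF coding. Labelled IPF showed the higher percentage throughout.

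Three stronger readings are not supported:

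- **Gaps of 20 points or more.** A model in which all patients share one IPF-coding rate gives, for example, 39.2% versus 18.6%. There the label carries no information except time observed, so this is an extreme illustration.
- **Near-certain statistical significance, judged from the 34,299 in the feasibility table.** That is a count of oxygen users under other criteria, with no IPF split, and is stated to be informational. It is not a stratum size.
- **That the whole-period label should be replaced.** The early-window rule does not classify better (about 9% wrong either way in the base case), and it may set aside about half of initiations.

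Underlying ILD type is also classified from the entire study period, as a declared exception. Its effect was not quantified, and no conclusion about Aim 2 is drawn from it.

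**What to change.** 1. In 7.6.1.1, state that follow-up oxygen use will not be reported or tested by IPF stratum as a crude percentage over variable follow-up. Report it as Kaplan-Meier or cumulative-incidence percentages at the fixed times already planned in 7.6.1.2. Do not rely on crude person-year rates alone, since these also differ when starts are front-loaded.
2. Report follow-up length by stratum, so that readers can see the imbalance.
3. Add to 7.8 that the IPF label depends on observation time, and that patients observed briefly default to non-IPF.
4. As a sensitivity analysis, repeat the stratified initiation analysis with IPF status taken from claims up to the second qualifying diagnosis (at least one IPF code) and follow-up starting there among oxygen-free patients. Alternatively, use a time-varying IPF indicator. State how many initiations fall before that date.

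**Cost.** Items 1 to 3 are wording and a choice of summary already in the plan. Item 4 is a little more analysis on existing claims. It does not reduce misclassification, and it sets aside about 15% of initiations under a constant hazard or 40 to 55% if starts cluster near diagnosis. It should therefore not replace the primary label.

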7.2.3 Study population: Aim 2 [REDACTED]

The analysis for Aim 2 and Further Aim will include patients identified for Aim 1 in Section 7.2.2 who meet the following additional selection criteria. Final oxygen therapy cohorts will be determined during the propensity score matching (PSM) procedure outlined in Section 7.6.2.2.

- **Oxygen therapy cohort**

- ILD patients with ≥ 1 medical claim for oxygen therapy after fibrosing ILD diagnosis. The ***index date*** will be defined as the first date of a claim for oxygen therapy.

- **No oxygen therapy cohort**
 - Matched to a patient in the oxygen therapy cohort. The **index date** will be assigned as a date that is eligible to set an index date (i.e., similar to the matched oxygen therapy patient in time from the fibrosing ILD diagnosis date to the index date, and during the same continuous enrollment period as the fibrosing ILD diagnosis date).

NOTE: Following review of results from Aim 1, the study team will determine whether criteria for Aim 2 and Further Aim require revision.

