7.3.2 Aim 2 Exposures

The exposure of interest is oxygen therapy versus no oxygen therapy among patients with fibrosing ILD and is defined based on evidence of oxygen therapy following ILD diagnosis, as described in Section 7.2.3.

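### In the visible text, the Aim 2 index date must fall in the same enrollment period as the ILD diagnosis for the no-oxygen cohort only, so an oxygen patient can be indexed after a coverage gap

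*Combined protocol and SAP*

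**What the plan says.** Section 7.2.3 gives the two Aim 2 cohorts different entry rules.

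- **Oxygen cohort.** The condition is "ILD patients with ≥ 1 medical claim for oxygen therapy after fibrosing ILD diagnosis". Section 7.3 places the index at "the first date following the fibrosing ILD diagnosis date with a claim with diagnosis for oxygen therapy". The abstract and the note to Figure 2 agree, and none of these places mentions enrollment.
- **No-oxygen cohort.** The index date must resemble the matched patient's in time since diagnosis and must lie "during the same continuous enrollment period as the fibrosing ILD diagnosis date". Section 7.3 repeats this as "a date within the same continuous enrollment period as the fibrosing ILD diagnosis date that is similar to the matched oxygen therapy patient", and the abstract carries the same condition.

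The enrollment rule that binds everyone is in Section 7.2.2: "Continuous enrollment with medical and pharmacy coverage for 12 months prior to the fibrosing ILD diagnosis date". The Aim 2 baseline in Section 7.3 is "The 12-month period prior to the index date", with no enrollment condition. Section 7.3.2 says that exposure "is defined based on evidence of oxygen therapy following ILD diagnosis, as described in Section 7.2.3".

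**The concern.** Two cohorts that are to be compared should be selected by the same rule. Here a patient may be diagnosed, lose coverage, return, and enter the oxygen cohort on the first oxygen claim after returning. No comparator can be given an index date after such a break.

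Three things are at stake.

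1. **Baseline.** Table 1 marks respiratory disease, comorbidity, medication use, HCRU and cost as claims variables, and Section 7.3.5.2 builds the respiratory, other clinical and Quan-Charlson covariates from codes on medical claims. Time without coverage would tend to read as absence of disease and of use.
2. **Index date.** Aim 2 asks about initiation of oxygen. After a gap, the first visible claim may be a continuation of oxygen that began while the patient was out of view.
3. **Consistency between aims.** Aim 1 follow-up stops at disenrollment, so Aim 1 would censor this patient as a non-initiator. Aim 2, read literally, would count the same patient as an initiator.

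**Working it through.** The plan states no figure on this point, so there is none to reproduce. The check sets the rules side by side and then counts baseline months.

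| Requirement | Oxygen cohort | No-oxygen cohort |
|---|---|---|
| 12 months enrolled before diagnosis (7.2.2) | yes | yes |
| Index in the same enrollment period as diagnosis (7.2.3, 7.3, abstract) | not stated | yes |
| 12 months enrolled before index (7.3) | not stated | not stated, but implied by the row above |

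**Comparators.** Let t ≥ 0 be the months from diagnosis to index. Enrollment is unbroken from 12 months before diagnosis through index, so covered time before index is 12 + t ≥ 12 months. Unobserved baseline is always 0.

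**Oxygen patients with a gap.** Let the gap last g months and end m months before index. Unobserved baseline months = max(0, min(g, 12 − m)). The gap lengths below are assumptions, because the documents give none.

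| Gap g (months) | m = 0 | m = 3 | m = 6 | m = 9 | m = 12 |
|---|---|---|---|---|---|
| 1 | 1 | 1 | 1 | 1 | 0 |
| 3 | 3 | 3 | 3 | 3 | 0 |
| 6 | 6 | 6 | 6 | 3 | 0 |
| 12 | 12 | 9 | 6 | 3 | 0 |

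**Example.** A patient is diagnosed in 2017, disenrolls in 2018, re-enrolls in January 2020 and has an oxygen claim in February 2020. The gap exceeds 12 months and m is about 1, so about 12 − 1 = 11 of the 12 baseline months are unobserved.

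Where m is 12 or more, the baseline is complete, but the true first oxygen claim could still have fallen inside the gap. The doubt about the index date is therefore wider than the doubt about the baseline.

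**How many patients?** The documents do not say. In Table 3, 80,151/212,466 = 37.7% met the pre-index step and 34,299/80,151 = 42.8% met the post-index step. The losses of 62.3% and 57.2% mix disenrollment, death, end of data and EHR inactivity under 6-month criteria. They do not estimate how often patients leave and return.

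**The case against.** The strongest reply is that oxygen initiation was meant to be seen only within Aim 1 follow-up. Section 7.3.1.1 says "Evidence of oxygen use will be captured in the pre-ILD baseline and Aim 1 follow-up periods", that follow-up ends at disenrollment, the Aim 2 patients are drawn from Aim 1, and the same section equates the index date with oxygen initiation. On that reading the example patient is a censored non-initiator in both aims. There is also a harmless reason for the difference in wording: an oxygen patient's index is an observed event, while a comparator's date has to be assigned and so needs its eligibility spelled out. Finally, Section 7.6.2.2, which fixes the final cohorts, is not in the public text, and the abstract speaks of Aim 2 enrollment criteria that may be revised after Aim 1.

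This reading is plausible, and the authors may have intended it. But it is not carried into the Aim 2 index definition, and Section 7.3.2 sends the reader to 7.2.3 rather than to the Aim 1 follow-up window. Comparators are Aim 1 patients too, yet the rule is written out for them. Section 7.6.2.2 may contain a restriction, and its absence from the public text is not a fault. A restriction there would still leave the visible definitions asymmetric.

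Three stronger inferences are tempting, and the documents do not support them.

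- **Sick oxygen users are matched to healthy comparators.** The propensity model is not visible. Section 7.8 describes matched patients as similar on pre-ILD characteristics, and that window is fully enrolled for everyone. If only those covariates enter the score, a later gap cannot blank them. Underlying ILD type is taken from the whole study period. On the other side, Table 1 and Section 7.3.5 also plan pre-index covariates, so the question stays open.
- **Survival through the gap biases mortality.** Follow-up starts at index in both cohorts, and comparators are aligned on time since diagnosis, so both have survived to index. No such bias is shown.
- **A specific covariate shift.** If 5–15% of oxygen patients entered after a gap, and a 40% prevalence were read as 10% in them, the cohort's recorded prevalence would fall by 0.05 × 0.30 = 1.5 to 0.15 × 0.30 = 4.5 percentage points. This is only the product of assumed inputs, and it does not translate into bias in any Aim 2 outcome.

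**Conclusion.** The point holds as a gap in the visible definitions. Taken literally, Sections 7.2.3 and 7.3 let an oxygen patient be indexed after a break in coverage and do not allow this for a comparator. For each affected patient, the loss runs from 0 to 12 of the 12 claims-based baseline months, and it is above 0 only when the gap overlaps the year before index. The index date may be late in either case, and Aims 1 and 2 can disagree about the same patient.

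The effect on the study cannot be sized. The number of gap patients is not given, and the effect on matching depends on whether the propensity score uses pre-index or pre-ILD covariates. The conclusion assumes that an analyst would follow 7.2.3 and 7.3 as written, and that Section 7.6.2.2 adds no restriction. If it does add one, what remains is a need to bring the definitions into line with it. The change is still worth making, because it is cheap and uses the plan's own rule.

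**What to change.** In Section 7.2.3, Section 7.3 and the abstract, require the oxygen cohort's index date to fall in the same continuous enrollment period as the fibrosing ILD diagnosis date, as for comparators. Align Section 7.6.2.2 with this, and report how many oxygen patients the rule removes.

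With 12 months already required before diagnosis and unbroken coverage from there to index, both cohorts then have a fully enrolled 12-month pre-index baseline. Aim 2 also counts as initiators only patients whose start of oxygen Aim 1 could have seen.

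The cost is one sentence in each place and one filter in the cohort program. The drawback is the loss of oxygen patients first seen after re-enrollment, whose index dates are the least reliable. The size of that loss is unknown until it is counted.

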7. RESEARCH METHODS

7.1 STUDY DESIGN

[figure not shown]
This is a non-interventional study of patients enrolled in a commercial, Medicaid, or Medicare plan, using existing administrative claims and EHR data in Optum's Market Clarity Integrated Claims + Clinical database for the period of 01 October 2015 through 30 June 2022 (study period). The study period may be extended through latest data available at the time of study implementation to increase study sample.

To describe the initiation and use of oxygen therapy after first fibrosing ILD diagnosis (**Aim 1**), patients aged ≥ 18 years with newly diagnosed fibrosing ILD will be identified from 01 October 2016 through 30 June 2022 (patient identification period). A schematic of the observation and identification periods is presented in Figure 1. Patients will be required to have 12 months of baseline continuous enrollment prior to fibrosing ILD diagnosis for collecting patient demographics and clinical characteristics. The pre-ILD baseline period will also be used to describe baseline prevalence of oxygen therapy use. Patients will be followed for a variable period from the fibrosing ILD diagnosis date (Section 7.2.2) until the earlier of disenrollment from the health plan, end of study period, or death. Oxygen therapy use will be described, and results will be stratified by underlying cause of fibrosis (e.g., IPF vs non-IPF ILD). Factors associated with initiation of oxygen therapy will be assessed using multivariable methods.

To assess the impact of oxygen therapy use on outcomes (**Aim 2 and Further Aim**), patients with fibrosing ILD who initiated oxygen therapy will be propensity score matched to those who did not yet initiate oxygen therapy. A schematic of the observation and identification periods is presented in Figure 2. The index date will be defined as the date of oxygen therapy initiation for oxygen therapy cohort, or a date that is eligible for index and is similar to the

[figure not shown]
matched case's index date for no oxygen therapy cohort. Disease progression, acute exacerbations, health care resource utilization (HCRU), and health care costs in the Aim 2 follow-up period will be described and compared between matched cohorts. Outcomes will be modelled using multivariable methods.

Figure 1. Observation and Identification Periods: Aim 1

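### Aim 2 starts the clock on a claim date for oxygen patients, but the visible rule does not tie a control's index date to any care contact, so early contact-recorded outcomes tilt against oxygen

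*Combined protocol and SAP*

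**What the plan says.** **Oxygen cohort.** Section 7.2.3 states that the index date "will be defined as the first date of a claim for oxygen therapy". Section 7.3.1.1 accepts as evidence of oxygen use at least one "diagnosis (ICD-10-CM), procedure (HCPCS, CPT), or revenue code for oxygen therapy". Time zero is therefore always a claim date.

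**Control cohort.** Section 7.2.3, like the abstract, calls for an eligible date and explains eligibility in a parenthesis opened by i.e. The date must be "similar to the matched oxygen therapy patient in time from the fibrosing ILD diagnosis date to the index date" and must fall "during the same continuous enrollment period as the fibrosing ILD diagnosis date". Section 7.3 repeats both conditions: "a date within the same continuous enrollment period as the fibrosing ILD diagnosis date that is similar to the matched oxygen therapy patient in time". Section 7.1 adds that oxygen patients are "propensity score matched to those who did not yet initiate oxygen therapy". No tolerance in days for a similar date is visible, and no claim, visit or encounter is required.

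**Start of follow-up.** Section 7.3 states: "The index date is the first day of follow-up observation time for Aim 2 and Further Aim". Matched pairs receive equal follow-up. No visible text sets a lag, leaves out index-day events, or excludes patients with hypoxemia or an exacerbation at index.

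**Outcomes.** Under Section 7.3.3.2, hypoxemia is the first evidence from ICD-10-CM codes or EHR data. An exacerbation is a CT claim with dyspnea recorded in the preceding 30 days and no listed alternative cause.

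**The concern.** The two cohorts enter follow-up in different states of observation. An oxygen patient's first day is generated by a claim, and the same episode of care can produce a saturation value, a dyspnea code or a CT. A control's first day, as visibly defined, may be any day in the enrollment period at about the right distance from diagnosis. On most such days nothing can be recorded.

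Two groups with identical disease and no oxygen effect would then separate in the first weeks, with oxygen looking worse. Section 5 says the study is to learn whether oxygen leads to better or worse outcomes, so a built-in tilt in one direction matters.

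The visible safeguards do not remove it. Equal follow-up within pairs aligns duration, not origin. Covariates from a 12-month baseline, or the pre-ILD characteristics that Section 7.8 names, do not align what happens on the index day.

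**Working it through.** The plan gives no event rates, visit rates, power or sample size formula, so there is no figure of its own to reproduce. The check is an illustration under no oxygen effect, with assumed inputs shown as ranges.

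**Inputs (all assumptions)**
- V = care days per year: 12, 24 or 52.
- p = chance that the outcome is recorded on a care day: 0.05, 0.10 or 0.20, the same in both cohorts.
- T = days of follow-up, with the index day as day one.

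**Formulas**
- Chance that an arbitrary day is a care day: V/365 = 3.3%, 6.6% or 14.2%. For the oxygen cohort it is taken as 100%.
- Chance of recording on an arbitrary day: q = pV/365.
- Control risk by day T: 1 − (1 − q)^T.
- Oxygen risk by day T: 1 − (1 − p)(1 − q)^(T − 1).

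**Example, V = 24 and p = 0.10**
- q = 0.10 × 24/365 = 0.006575.
- Control, 30 days: 1 − (0.993425)^30 = 18.0%.
- Oxygen, 30 days: 1 − 0.90 × (0.993425)^29 = 25.7%.
- Ratio: 25.67/17.96 = 1.43. At 365 days the risks are 91.9% and 91.0%, ratio 1.01.

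**Full grid (risk ratio, oxygen vs control)**

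| V | p | 30 days | 365 days |
|---|---|---|---|
| 12 | 0.05 | 1.96 | 1.06 |
| 12 | 0.10 | 1.93 | 1.04 |
| 12 | 0.20 | 1.89 | 1.02 |
| 24 | 0.05 | 1.45 | 1.02 |
| 24 | 0.10 | 1.43 | 1.01 |
| 24 | 0.20 | 1.39 | 1.00 |
| 52 | 0.05 | 1.18 | 1.00 |
| 52 | 0.10 | 1.16 | 1.00 |
| 52 | 0.20 | 1.13 | 1.00 |

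The model fits hypoxemia most directly. An exacerbation needs two linked records, so for that outcome it shows direction rather than size.

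**After anchoring.** If the control's index day is also a care day, both cohorts have risk 1 − (1 − p)(1 − q)^(T − 1), and the ratio is 1.00 in every cell. This relies on p being equal on both index days.

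**Separating out acute illness.** A different model asks what happens if oxygen also tends to start during acute illness. Assume:
- a share s = 0.5 to 0.9 of oxygen index dates are acute respiratory contacts;
- event risk is m = 2 to 3 times higher for 30 days after such a contact;
- patients have a = 1 to 3 acute contacts and 20 to 50 contact days of any kind per year.

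With r = 1 − exp(−30a/365), the relative 30-day event rate for a control on an arbitrary date is C = 1 + r(m − 1). For oxygen it is sm + (1 − s)C. The ratio runs from 1.32 (s = 0.5, m = 2, a = 3) to 2.43 (s = 0.9, m = 3, a = 1).

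Now index controls on any claim day. A fraction f = a/V of those days is acute, from 1/50 = 2% to 3/20 = 15%, and the control rate becomes fm + (1 − f)C. The ratio falls only to 1.20 to 2.36. Across the grid, 60 to 96% of the excess remains. That part comes from acute illness at oxygen start, not from the missing claim anchor.

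**The case against.** **The visible definition may not be the whole rule.** Section 7.2.3 sends final cohort formation to Section 7.6.2.2, which is not in the public text. Section 7.1, the Figure 2 notes and the abstract's study design text list being eligible and being similar as separate conditions, which may hint at a further criterion. A note in 7.2.3 also allows the Aim 2 criteria to be revised after Aim 1. This stands. A reader might infer that the plan has no encounter rule at all, but the documents show only that the visible definition contains none. The i.e. wording still reads as the eligibility rule, so any further rule should appear in 7.2.3 and 7.3.

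**Oxygen claims are not shown to be sick visits.** A reader might infer that oxygen usually starts at a contact made because the patient is unwell, and so quote the 1.32 to 2.43 range as the size of this problem. The documents do not say so. Any one code qualifies, and a supply claim need not be a visit. Most of that range is also confounding by indication, and Section 7.8 already concedes residual or unobserved confounding. This stands in full.

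**Some index-time severity is captured.** Table 1 includes hypoxemia in the pre-index baseline, and Sections 7.3.5.2 and 7.3.5.3 include acute respiratory failure, pneumonia and utilization. Worsening before the oxygen claim can be balanced if these enter the propensity score. New status on the index day cannot.

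**The effect is early and affects some outcomes only.** By one year it is at most about 6% in the illustration. Section 7.3.3.2 classes hypoxemia and exacerbations as secondary, although the abstract lists them as primary. This limits the weight of the point but does not remove it.

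**Conclusion.** The point holds for the rule as visibly written. One cohort's time zero is a claim date, the other's need not be, and the index day counts as follow-up. For outcomes recorded through care contacts this pushes early comparisons against oxygen: illustratively a 30-day risk ratio of 1.13 to 1.96 with no true effect, and 1.00 to 1.06 at one year. Those figures rest on assumed visit and recording rates, on treating the oxygen claim date as a care day, and on equal recording chances per care day in both cohorts.

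FVC progression is less directly affected. A reader might infer that mortality is biased in the same way. It is not: excess early deaths would come from acute illness at oxygen start, which is confounding by indication and would largely remain after the change. This is a cheap improvement and does not show that the Aim 2 comparison is invalid.

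**What to change.** Unless Section 7.6.2.2 already does so, make these changes.

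1. In Sections 7.2.3 and 7.3, require the control's index date to be a date with a medical claim, within a stated number of days of the matched oxygen patient's time since diagnosis. Match care setting (inpatient or ED versus outpatient) where feasible.
2. Add a sensitivity analysis of the Aim 2 outcomes that starts counting events after the first 30 days in both cohorts, among pairs still under follow-up.

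If Section 7.6.2.2 already contains such a rule, restate it in 7.2.3 and 7.3.

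The data already exist, so the cost is wording and programming, plus the loss of controls with no claim in the window. A stricter rule that needs an acute respiratory contact would address more of the acute-illness component, but it is a real trade-off. At an assumed 1 to 3 such contacts a year, only 1 − exp(−60/365) = 15% to 1 − exp(−180/365) = 39% of controls would have one in an assumed 60-day window, and the comparison population would change.
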